Screening and Eligibility Assessment	19
Informed Consent	19
8.3 Objection by minors or incapacitated subjects	20
8.4 Benefits and risks assessment, group relatedness	20
9. ADMINISTRATIVE ASPECTS, MONITORING AND PUBLICATION	21

COORDINATE

9.1	Handling and storage of data and documents	21
9.2	Monitoring and Quality Assurance	21
9.3	Annual progress report	22
9.4	Temporary halt and (prematurely) end of study report	22
9.5	Public disclosure and publication policy	22
10.	STRUCTURED RISK ANALYSIS	22
11.	REFERENCES	22

COORDINATE

LIST OF ABBREVIATIONS AND RELEVANT DEFINITIONS

AI	Assistant Investigator
CA-ARTI	Community Acquired Acute Respiratory Tract Infection
CRF	Case Report Form
CRP	C-reactive protein
CRP POCT	C-reactive protein point-of-care testing
COVID-19	Coronavirus disease 2019
FMC	Family Medicine Centre
FOP	Feldsher-Obstetric Point
FPG	Family physicians groups
GP	General Practitioner
HCW	Healthcare Workers
IC	Informed Consent
ICU	Intensive care unit
IMCI	Integrated management of childhood illness
IRCT	Individual Randomised Controlled Clinical Trial
PI	Principal Investigator
RCT	Randomised Controlled Clinical Trial
RTI	Respiratory Tract Infection
SAE	Serious Adverse Event
SARS-CoV-2	Severe Acute Respiratory Syndrome Coronavirus-2 (virus causing COVID-19 disease)
SD	Standard deviation
SMG	Study Management Group
UCPH	University of Copenhagen
WHO	World Health Organisation

SUMMARY

Rationale: Respiratory tract infections are the most common cause to contact to the healthcare system worldwide and the most common cause of inappropriate use of antibiotics. And while lower respiratory tract infections are still the main cause of death for children under 5 globally, only a small proportion of children with airway disease need antibiotics.

Overuse of antibiotics globally is leading to increasing rates of antibiotic resistance and may lead to a 'post-antibiotic' era. Case fatality rates for pneumonia in children remain high in Central Asia and there is a lack of knowledge of which viruses and bacteria cause the disease. Antibiotic resistance patterns of common bacteria remain largely unknown in Central Asia which makes it challenging for clinicians to choose the right antibiotic to treat children with suspected bacterial pneumonia and sometimes healthcare workers overuse an antibacterial therapy even when the child does not need it.

Randomised trials of using CRP point of care test (POCT) to guide antibiotic prescription for respiratory tract infections has been successful in lowering unnecessary antibiotic prescriptions in adults in high income countries but left a small concern for safety in the form of possibly slightly increased risk of hospitalisation in the CRP group.

Objective: This study seeks to gain evidence on whether use of C-reactive protein point-of-care test can safely decrease prescription of antibiotics for children under 12 with acute respiratory symptoms in primary level healthcare centres in Kyrgyzstan.

Study design: Multicentre, open-label, individual randomised controlled clinical trial with 14 days blinded follow-up in rural Chui and Naryn regions of Kyrgyz Republic. Healthcare workers from ten selected healthcare centres will be trained in the CRP POCT and in interpreting the results in the field.

Study population: Children aged from 6 month to 12 years attending the primary level healthcare centres during normal business hours with acute respiratory symptoms.

Main study parameters: The proportion of patients in the two groups prescribed an antibiotic within 14 days of index consultation; length of disease, antibiotics given at index consultation, admissions and vital status.

Nature and extent of the burden and risks associated with participation, benefit and group relatedness: Risks, inconvenience and burden associated with participating in this observational study are low. As part of the inclusion children in the CRP cluster group will have a finger-prick test performed. This may be unpleasant and cause transient discomfort but poses no risks to the child. Follow-up will be three short phone calls day 3, 7 and 14 after inclusion. Risks includes possible undertreatment of serious disease, however previous studies have not found safety issues with CRP testing in children. There is no direct benefit to participants, but side effects and non-necessary medications are likely minimised.

1. INTRODUCTION AND RATIONALE

Respiratory tract infections are the most common cause of contact to the health system and are the main reason for antibiotic overuse at the primary care level globally [1–3]. At the same time, acute lower respiratory infections (ALRI) are the most common cause of death among children under 5 globally [4], costing the lives of almost 1 million children annually [5]. Unfortunately, there is substantial overlap in the presentation of different causes of acute lower respiratory illness in young children, including bacterial pneumonia, viral infections and wheezing [6,7] and with increasing coverage of pneumococcal and Haemophilus influenza type b vaccination, only a smaller proportion of these need antibiotics [8,9]. At the same time, globally, most children are diagnosed and treated at a primary care clinic, primarily by mid-level providers with only limited access to diagnostic equipment [3]. To assist healthcare providers in diagnosing under these conditions, various algorithms have been used, e.g. WHO’s Integrated Management of Childhood Illness, which bases diagnosis of respiratory diseases in children mainly on presence of cough and elevated respiratory rate [10]. This approach has been shown to severely over-diagnose pneumonia and thus result in unnecessary prescription of antibiotics [11]. Therefore, new approaches to diagnosing and treating respiratory infections in children are urgently needed.

Concurrently, antimicrobial resistance is now what WHO calls a global health emergency and warns that ‘A post-antibiotic era—in which common infections and minor injuries can kill—far from being an apocalyptic fantasy, is instead a very real possibility for the 21st century [12] (Figure 1). Unnecessary prescription of antibiotics is extensive globally [2,12] and most healthcare providers are aware of the global threat of antimicrobial resistance but express the need for support for prescribing differently, such as knowledge of local resistance patterns of pathogens and better diagnostics to support a decision not to treat with an antibiotic [13].

[figure not shown]

Figure 1: Deaths attributable to antimicrobial resistance every year by 2050 (Source: BBC and Review on Antimicrobial Resistance – Tackling a Crisis for the Health and Wealth of Nations (2014)).

COORDINATE

C-reactive protein (CRP) is an acute phase reactant produced by the liver which can be used as a marker of serious infection. Randomised trials of using CRP point of care test (POCT) to guide antibiotic prescription for respiratory tract infections has been successful in lowering unnecessary antibiotic prescriptions in adults in high income countries but left a small concern for safety in the form of possibly slightly increased risk of hospitalisation in the CRP group [14]. Trials of CRP POCT in children have been performed in Tanzania as part of an intervention package with a strict prescription limit of > 80 mg/L CRP with a reduction in antibiotic prescriptions from 40% to 2% [15]. In South-East Asia with a small but statistically significant effect (5% reduction) when used as either above or below a certain threshold (40 mg/L) in Thailand and Myanmar [16]. In a sub-group analysis from a trial in Vietnam with both children and adults where the numeric value of CRP was used after a short training in CRP interpretation along with clinical evaluation resulted in a 20% reduction from 64% to 44% [17]. A cross-cutting qualitative study of the above-mentioned studies in Thailand, Myanmar, and Vietnam showed that lack of non-antibiotic alternatives to prescribe led to lower adherence to the CRP POCT result [18].

As the intervention of supplying CRP POCT to healthcare providers is more a behavioural than biomedical, previous trials have recommended that further trials are done in different contexts and that qualitative studies of reasons for success or failure [17].

Central Asian countries have been underrepresented in health science, especially in primary care research. The clinical context of primary care in South-East Asian countries, like Vietnam, Thailand, and Myanmar, and Central-Asian countries, like Kyrgyzstan, are vastly different with different caseloads, different human resources, and varying time for consultations available [3]. At the same time, case fatality rates for pneumonia in children remain high in Central Asia (Figure 2) and there is a lack of knowledge of which viruses and bacteria cause the disease. Antibiotic resistance patterns of common bacteria remain largely unknown in Central Asia, which makes it challenging for clinicians to choose the right antibiotic to treat children with suspected bacterial pneumonia.

[figure not shown]

Figure 2: Causes of Death in Children under 5 in Central Asia.

COORDINATE

Figure 3 shows a graph of the distribution of morbidity in children aged 0 to 14 years in the Kyrgyz Republic (<http://cez.med.kg/>) with respiratory diseases being the most common (49,7%). Among all acute respiratory diseases in children, upper respiratory tract infections are the most common, as shown in Figure 4. The number of cases per 100,000 population seems to de-crease by 2020, but it is still quite high (<http://cez.med.kg/>).

[figure not shown]

Figure 3: The structure of morbidity in children from 0 to 14 years old in the Kyrgyz Republic (%) 2012-2020

[figure not shown]

Figure 4: Dynamics of the prevalence of acute respiratory diseases in children under 14 years of age (per 100,000 child population) in the Kyrgyz Republic (2009-2020)

2. OBJECTIVES

The aim of this project is to find out if the overuse of antibiotics in children with acute respiratory symptoms can be reduced by effectively identifying children at increased risk of infections who require antibiotic therapy and children who will not benefit from antibiotics. This is done by implementing CRP POCT at the primary healthcare level.

Hypotheses:

Supplying CRP POCT equipment to primary healthcare providers will help them identify the majority of children who suffer from viral infections and assist in withholding antibiotic treatment when no benefit can be expected and will help identify the severely sick children in need of urgent referral, thus lowering unnecessary use of antibiotics and improving primary care management by studying supplying supportive medication for those not in need of antibiotics.

It will be an individually randomised clinical trial where CRP POCT is supplied to approximately 14 healthcare centres. All children up to 12 years with respiratory symptoms have basic clinical data recorded as well as data needed to classify according to WHO IMCI pneumonia diagnostic criteria. CRP POCT is used at intervention sites and CRP results, diagnosis, and treatment is recorded. Follow-up phone calls will be made 3, 7 and 14 days after the health centre visit to record recovery, antibiotics use, hospitalisation and vital status of the participating children.

3. STUDY DESIGN

Multicentre, open-label, individual randomised controlled clinical trial with 14 days blinded follow-up will be conducted in low altitude Chui and high altitude Naryn regions of Kyrgyz Republic. Healthcare workers (HCW) from 14 randomly selected healthcare centres will be trained in the CRP POCT and in interpreting the results in the field.

Children will be screened at 14 randomly selected primary healthcare centres using a screening form (see Appendix A). The 14 healthcare centres will consist of a combination of Family Medical Centres, Family Physician Groups and Feldsher-obstetric points. Screening will be performed by an assistant investigator (AI) prior to the children being examined by a local HCW. The screening form will include a list of symptoms from the eligibility criteria. If a child has at least one symptom from the inclusion criteria, the AI will receive a rapid diagnostic test for SARS-CoV-2 at the HCW's office. In case the test is negative, AI will ask the parent/caregiver about their child's participation in the study and offer to read and sign the informed consent (IC) form. Otherwise (the test is positive), the child will not be included in the study. If the parents agree to their child's participation in the study and have signed IC, the child is enrolled in the study and randomised to Group A or Group B. The randomisation will be carried out by a responsible person located in the Bishkek office through the Sealed Envelop™ programme (www.sealedenvelope.com). This person will be in touch with AIs by telephone and, upon the request of the AIs, will remotely randomise and report the result to AIs. The principal investigator will not to be aware of the results of the randomisation and follow-up will be blinded as well.

COORDINATE

Group A:

[figure not shown]
Participants assigned to Group A will take CRP POCT during a check-up with their HCW. The AI will attend the child's consultation with the local HCW and complete the case report form (CRF) (see Appendix C). Consequently, the CRP result will be recorded in the CRF, which will be the basis for choosing a treatment, depending on its result.

Group B:

HCWs will also consult children who have been randomised to Group B. The AI will complete the CRF for these children, but no CRP POCT test will be performed in this control group. They will receive the treatment prescribed by the HCW as usual care in an intention-to-treat model.

Both groups will be assessed additionally on the 3rd, 7th and 14th day by phone calls from another AI who is blinded to the group allocation using Follow-up questionnaires (see Appendix E).

The RCT study design is depicted in figure 5:

COORDINATE

Figure 5: Multicentre, open-label, individual randomised controlled clinical trial with 14 days blinded follow-up.

PILOT STUDY

Prior to the start of the Main Study, a pilot study will be conducted to qualify and ensure practicality and acceptability of the main study. We aim to include 5-10 % of the original sample size calculation, approximately 60-75 (5%) children. The pilot study will assess the number of eligible children and determine the number of caregivers willing to provide the informed consent form.

In the pilot study we will see how the CRFs and follow-up interviews are executed in regard to time to complete, understanding the questions and ease of use, completeness and loss to follow-up.

The pilot study will also involve qualitative interviews in the form of focus groups with healthcare workers and child caregivers.

The pilot study will be carried out in the three different first level of healthcare system in Chui region of Kyrgyzstan, in three randomly selected villages. This will inform how the trial will work, whether or not the project will be acceptable and feasible and likely to provide the results within the designated time.

4. STUDY POPULATION

4.1 Population (base)

All patients aged from 6 month to 12 years attending the primary care health clinics during normal business hours with symptoms as described in the inclusion criteria.

Patients of both sexes and all ethnic background can be included.

4.2 Inclusion criteria

Inclusion criteria is:

- Between 6 month and 12 years of age;
- Parents/caregivers of a child are able and willing to comply with all study requirements;
- Parents/caregivers of a child is able and willing to give Informed Consent;
- Having at least one of the following focal symptoms lasting for less than 2 weeks:
 - Cough;
 - Fast/difficult breathing;
 - Sore throat;
 - Shortness of breath;
 - Wheezing

4.3 Exclusion criteria

COORDINATE

A potential subject who meets any of the following criteria will be excluded from participation in this study:

- Severely ill and in need of urgent referral where measurement of CRP POCT would delay the process;
- Terminally ill patients;
- Patients with ear ache only;
- Patients with known immunosuppression or severe chronic disease (HIV, liver disease, history of neoplastic disease, long term systemic steroid use or similar conditions as assessed by the health worker or AI);
- Parents/caregivers who are not able to participate in follow-up procedures (lack of telephone etc);
- Positive rapid diagnostic test for SARS-CoV-2;
- Haven taken antibiotics within 24 hours before the index consultation

4.4 Sample size calculation

Provisional calculations show that a power of 90% to detect a 10% reduction in antibiotic use (from 55% to 45%) at a statistical significance level of 0.05 is achievable with the available resources resulting in recruitment of approximately 1046 children, 523 in each arm. With an expected dropout rate of 15% we aim to include 1204 children in total, 602 in each arm.

We expect to be able to include a sufficient number of patients in approximately three months. Each clinic has a patient flow of approximately 10 – 25 children per week. With 14 clinics, the weekly flow of potential participants is 100 – 250 even if only less than 1 in 2 patients are enrolled; we will still keep our schedule.

There has not been a diminished flow of patients at the healthcare centres during the COVID-19 pandemic, so the study should be able to move ahead on schedule even in the face of the pandemic.

5. TREATMENT OF SUBJECTS

Children with the relevant age and symptoms will be consulted by a researcher, and with the consent of the parent / caregivers the child will be included in the study. In this case, the child in the control group will receive treatment according to the usual recommendations of the health workers. A child in the intervention group will receive an antibiotic only in accordance with the results of the CRP and the assessment of the health worker. If the child does not need antibiotic therapy, treatment will be prescribed in accordance with the recommendations for the management of acute respiratory viral infections without prescribing antibiotics, prescribing e.g. acetaminophen or other supportive treatment.

6. Intervention

CRP POCT equipment will be supplied at healthcare centres, along with a short training in use and interpretation supporting the clinical evaluation of the child. It will be communicated that CRP levels less than 10 indicate that the disease is not severe, and antibiotics is most likely not needed, if between 10 and 50, that antibiotics might be needed, and if more than 50 that it

COORDINATE

is likely that they are needed. With CRP between 10-50 the HCW are instructed to take the clinical picture into account together with the value of the test. With obvious symptoms of bacterial infection such as high fever, very affected general condition, purulent sputum, signs of acute otitis media, persisting rhinosinusitis over 10 days etc. The training will also include knowledge of CRP pharmacodynamics and cases where a low CRP might need to be interpreted cautiously, e.g. a history of fever lasting less than 24 hrs. HCWs will be instructed to use CRP POCT for all patients in the intervention group and use the information to guide diagnosis and treatment choice. We will use Aidian (Copenhagen, Denmark) QuickRead go CRP POCT set-up (Figure 3).

Figure 3: Aidian CRP POCT.

7. METHODS

7.1 Study parameters/endpoints

The primary outcome of the randomised trial is antibiotic prescription within 14 days from the index consultation, measured as proportion of children in each study group who receive an antibiotic (superiority analysis).

However, any reduction in antibiotic use must be balanced without any compromise to patient safety and the study will therefore include two primary outcomes. The second primary study outcome is patient safety measured as the number of days until recovery (non-inferiority analysis).

Secondary outcomes include other treatment, antibiotics given at index consultation, re-consultations, admissions and vital status.

7.2 Study setting

The study will be conducted in primary care in the rural areas in Chui region of Kyrgyz Republic, a Central Asian mountainous lower middle-income country with 6.2 million inhabitants (Figure

COORDINATE

3). The study will be conducted in 14 randomly selected healthcare centres and consist of villages with between 590 and 10764 inhabitants. From previous research in the areas, we know that during winter-time on average, approximately 25 children visit a health centre with respiratory symptoms per week [3].

7.3 Types of medical centres in Kyrgyzstan

The Family Medicine Centre (FMC) is a unified complex, which employs doctors of all specialties and provides outpatient treatment for patients belonging to the area. The FMC also provides basic diagnostic services (general and biochemical blood tests, urine tests, stool analysis, electrocardiography, echocardiography, X-ray and ultrasound).

Family physician groups (FPG) is a medical institution that brings together family doctors, therapists, pediatricians, obstetrician-gynecologists, nurses and paramedics (depending on the population in the area and staffing), providing primary health care for patients related to the area. If it is necessary to take clinical tests, blood, urine or stool are taken from the patient and sent to the FMC. Results come in a few days. If it is necessary to pass biochemical tests or to undergo an instrumental examination, the patient is sent for this to the FMC or, if necessary, for a consultation with a narrow specialist.

A feldsher-obstetric point (FOP) is a structural unit of a medical and preventive institution that provides pre-hospital primary health care in rural areas, where feldshers and nurses act as medical personnel. In FOPs, pre-medical examination of patients belonging to this village is carried out. If it is necessary to consult a family doctor, the patient is referred to the FPG. There is no diagnostic equipment in FOPs.

A feldsher is a medical specialist who occupies an intermediate position between a doctor and a nurse. He can work both under the guidance of a doctor and independently.

7.4 Randomisation, blinding and treatment allocation

Randomisation will occur through a web based service Sealed Envelope™ <https://www.sealedenvelope.com/> and conducted in a designated room by a dedicated member of the research team. Participants will be randomised (1:1) to either standard care or care according to CRP POCT. A dedicated member of the research team will inform the assessors of group allocations via telephone.

7.5 Study procedures

Recruitment:

The recruitment of participants will be carried out at 14 selected health centres among the children in attendance. AI screening will be used to select patients with the symptoms described in the STUDY POPULATION section. Further, in case the child is eligible for the

COORDINATE

study, the AI will ask the parent / guardian about their child's participation in the study and offer to read and sign the IC form.

Special requirements during the COVID-19 Pandemic:

Given the COVID-19 pandemic, a Safety Concept for the COORDINATE Project has been developed. Due to the current situation with COVID-19, the following requirements must be observed for the study:

1. Participants and HCWs must wear disposable masks;
2. The consultation room and corridors should be equipped with alcohol-based wall sanitisers;
3. Cleaning in the room and in the corridors should be carried out strictly using chlorine solution;
4. Participants (children and caregivers), hospital staff and research group must maintain social distance and refrain from close contact;
5. All children included in the study will receive a rapid diagnostic test for SARS-CoV-2

Screening and Eligibility Assessment

Children aged 6 month to 12 years will be assessed against the inclusion criteria by an AI and if eligible, be included upon signing of an IC by their parents/caregivers and have their CRF completed on paper. The AI will have a screening form. (See Appendix A) The selected children will then be randomised via a web programme (www.sealedenvelope.com) into two groups: Group A, who will receive antibiotics prescribed according to CRP POCT and provision of alternative non-antibiotic supportive treatment (e.g. paracetamol and/or salbutamol as relevant) for children with respiratory diseases that do not need antibiotics and Group B, who will receive the usual care.

Informed Consent

When the patient consults at the healthcare centres, explanation of the study, provision of study-related information, patient information sheet and IC will be performed at the practice. All study personnel will be trained by the national network facilitator or Principal Investigator (PI), detailing no less than: the exact nature of the study, implications and constraints of the study, and risks and benefits of participation. The study will provide a patient information sheet (appendix D) that includes all necessary information available in the official national language. 10 minutes will be given to the parents/caregivers to consider the information given to them and to ask any questions they may have about the study to decide whether their child will participate in the study. As participants are not of legal age of consent in their jurisdiction, consent will be provided by their parent/caregiver. It will be clearly stated in the patient information sheet and verbally explained to the participant that they are free to withdraw from the study at any time for any reason without impacting their future care, and with no obligation to provide the reason for withdrawal.

COORDINATE

Study Visit – Inclusion

Patients will be included when they attend the health clinic upon fulfilment of the above-mentioned criteria. During the consultation and upon IC the baseline CRF data will be gathered (see appendix A, for the exact information that will be recorded). The CRF will be completed by the AI; the examination will be carried out by the clinic's HCW.

- Demographic details including: sex, age, co-morbidities, BMI category;
- Duration of CA-ARTI symptoms prior to consulting;
- Presence of specific RTI and general symptoms;
- Overall severity rating (HCW perception);
- Clinical assessments and results of clinical examination (oxygen saturation, respiratory rate, blood pressure, heart rate, body temperature);
- All diagnostic tests performed or ordered;
- Management: antibiotic, antiviral prescription, other (symptomatic) medication prescribed and advised;
- Additional advices: preventive measures for themselves and their family members, time-off, home isolation, hygienic measures;
- Referral to hospital or public health authority;
- During this visit a swab will be taken see below;
- COVID-19-specific questions;
- Participants randomised to a control group will receive routine care. Participants randomised to the CRP group will take the CRP test

Follow-up with Phone Calls

There will be no scheduled follow-up visit at the health clinic required by the study. Parents/caregivers will be phoned 3, 7 and 14 days after the index consultation to record outcomes. Phone calls will be blinded and performed by another AI (see appendix D):

- Number of symptomatic days after the consultation;
- Duration of specific symptoms;
- Return to school/work and usual activities;
- Additional contacts with HCWs;
- Any medicine bought over-the-counter or prescribed by other HCWs including the name of the drug(s);
- Additional diagnostic testing, including SARS-CoV-2 and outcomes;
- Complications (hospitalisation -days in hospital, ICU, medication/oxygen/ventilation received there-, pneumonia, death);
- Infections in their households;
- General well-being;
- Diarrhea

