7.12 General principles

This study is designed as an RCT to test effectiveness of CRP POCT in lowering prescription of antibiotics to children from 6 month to 12 years of age in 14 primary health clinics in Kyrgyzstan presenting with acute respiratory tract infection (see protocol for inclusion criteria) without compromising patient safety. The children will be randomised into two groups: in the intervention group CRP POCT will be measured and used to guide clinical decision-making regarding antibiotic use, in the control group standard care will be performed without CRP measurement. The primary outcome is the proportion of children receiving antibiotics within 14 days from the index consultation in each study arm. The main statistical analysis will follow an intention to treat (ITT) principle, in which all enrolled children will be analysed in the groups they are randomised to. Safety outcomes as well as other secondary outcomes will be assessed as described in 1.2.

The statistical analysis will be performed after data from the last follow up has been entered. Analysis will be performed by the investigators of the study using SAS statistical software. Data will be stored in REDcap.

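### The plan does not settle whether supplied supportive medicines are part of the Group A intervention; if they are, the trial estimates CRP testing plus that supply, and no planned analysis would show supportive treatment by arm

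*Combined protocol and SAP*

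**What the plan says.** Two places bring supportive medicines into the intervention. The screening and eligibility part of section 7.5 adds to CRP-guided antibiotics in Group A the "provision of alternative non-antibiotic supportive treatment (e.g. paracetamol and/or salbutamol as relevant) for children with respiratory diseases that do not need antibiotics"; the comparator is "Group B, who will receive the usual care". The hypothesis in section 2 speaks of "supplying supportive medication for those not in need of antibiotics".

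Elsewhere the arms are described without any supply of medicines. Section 3 says "Participants assigned to Group A will take CRP POCT during a check-up with their HCW" and, for Group B, "no CRP POCT test will be performed in this control group". Section 6 lists equipment and a short training. Section 7.4 contrasts standard care with CRP-guided care. The study-visit list in 7.5 assigns the CRP test to one group and routine care to the other. SAP 7.12 sets out to test CRP POCT and says "in the control group standard care will be performed without CRP measurement".

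Section 5 lies between the two. Directly after the sentence on the intervention group, it says that a child who needs no antibiotic is prescribed supportive treatment. It does not say that the study supplies it.

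On outcomes, section 7.1 states: "Secondary outcomes include other treatment, antibiotics given at index consultation, re-consultations, admissions and vital status". The SAP list in 7.15 and the analyses in 7.21 include antiviral treatment but no other supportive or symptomatic treatment.

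**The concern.** Followed as written, section 7.5 delivers a two-part strategy, which SAP 7.12 would report as the effect of CRP POCT. The protocol gives its own reason to care about the second part. The Introduction reports from a qualitative study in three countries that "lack of non-antibiotic alternatives to prescribe led to lower adherence to the CRP POCT result". Access to alternatives may therefore alter how far a CRP result is followed, and so the first primary outcome, antibiotic prescription within 14 days. The second primary outcome, days until recovery, could also be touched if symptomatic medicines were more available in one arm.

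What is at stake is the wording of the conclusion. A health system that adopts CRP testing without the medicines would be relying on a result obtained with them. Sites that read the sections differently could also deliver different interventions.

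**Working it through.** **Step 1: the arm definitions side by side.**

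| Place | Group A | Group B | Supply of supportive medicines? |
|---|---|---|---|
| Section 2, hypothesis | CRP equipment for providers | not described | Yes, arm not stated |
| Section 3 | CRP test, result guides treatment | Usual care, no CRP test | Not mentioned |
| Section 5 | Antibiotic according to CRP and clinical assessment | Usual recommendations | Prescribed; supply not stated |
| Section 6 | Equipment and training | not described | Not mentioned |
| Section 7.4 | CRP-guided care | Standard care | Not mentioned |
| Section 7.5, screening | CRP-guided antibiotics and provision | Usual care | Yes, Group A |
| Section 7.5, study visit | CRP test | Routine care | Not mentioned |
| SAP 7.12 | CRP guides antibiotic use | Standard care, no CRP | Not mentioned |

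No section says that Group B receives the same provision, and none says that it is denied it.

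**Step 2: what the contrast estimates under each reading.** Let C be the effect of CRP testing at equal access to medicines, and S the further effect of providing medicines to children managed with CRP.

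- Ordinary prescribing, equal access in both arms: contrast = C. More supportive treatment in Group A would then be a consequence of CRP-guided decisions and part of C.
- Supply to Group A only: contrast = C + S.

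Two arms give one contrast, so C and S cannot be separated within the trial.

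**Step 3: the plan's own sample size.** Section 7.16 uses 55% against 45%, 90% power and a 0.05 level. With the pooled two-sided formula,

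n = [1.960·√(2·0.50·0.50) + 1.2816·√(0.55·0.45 + 0.45·0.55)]² / 0.10² = (1.3859 + 0.9017)² / 0.01 ≈ 523.3 per arm.

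This agrees with the stated 523 (1046 in total). The arithmetic is not in question. The 10 points are attributed to CRP POCT with no allowance for a second component.

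**Step 4: illustration only.** The documents give no effect for the medicines, so every S below is an assumption, and S = 0 is within the range.

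- Prescribing. If 0, 1, 2, 3 or 5 of the 10 points were S, CRP alone would give 10, 9, 8, 7 or 5 points. With 523 per arm, the power to detect an effect of that size is 90%, 83%, 74%, 62% or 37%.
- Recovery. Take the SD of 5 days and 1-day margin from 7.16 and the 95% interval from 7.19 (taken as two-sided). The standard error with 523 per arm is 5·√(2/523) = 0.309 day. Suppose CRP alone lengthened recovery by exactly 1 day and medicines shortened it by b days. The chance of declaring non-inferiority is Φ(b/0.309 − 1.960): 2.5%, 12%, 37% or 68% for b = 0, 0.25, 0.5 or 0.75.

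**Step 5: would the plan show a difference in supportive care?** The study-visit list in 7.5 records symptomatic medication prescribed and advised. The follow-up calls record medicines bought or prescribed elsewhere. Section 7.1 names other treatment as an outcome. Sections 7.15 and 7.21 carry forward only antivirals.

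**The case against.** The strongest reply is that supportive treatment here is simply what a clinician prescribes after deciding against an antibiotic. Section 5 uses the language of prescribing, section 6 lists no drug supply, and 7.4 names a management strategy. Both arms are seen by health workers at the same centres, and nothing says that usual care lacks paracetamol or salbutamol. On that reading there is no separate co-intervention. This stands as a possible reading. It does not remove the conflict, because 7.5 names provision for Group A as a component beside the CRP result, and section 2 speaks of supplying.

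Three stronger inferences are tempting, and the documents do not support them.

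- A reader might infer that any effect certainly cannot be credited to CRP. That requires supply to Group A only, which is not settled. No section states that CRP is the only difference either; several imply it by naming nothing else.
- A reader might size the contribution from the Introduction, setting a fall from 40% to 2% in a package trial against reductions of 5% and 20% elsewhere. The Introduction does not say what the package contained, and those trials also differ in threshold, population and setting. The contrast says nothing about supportive medicines.
- A reader might treat the qualitative finding as proof that medicines reduce prescribing by themselves. It concerns adherence to the CRP result. Likewise, no section gives an effect of these medicines on recovery.

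It is also fair to say that the data would exist and that antivirals are analysed. The gap is one stated outcome without a planned analysis.

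**Conclusion.** The point holds conditionally. The sections disagree on whether provision of supportive medicines is part of Group A's intervention, and the documents do not resolve it. If supply is for Group A only, randomisation still gives a valid comparison of the arms as delivered, but both primary results belong to CRP POCT plus provision. With equal access, the attribution problem largely disappears. No size is claimed: the share due to medicines cannot be derived from the documents, and the scenarios above rest on assumed values.

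The second part does not depend on that answer. Other treatment is promised in 7.1 and, antivirals apart, has no place in 7.15 or 7.21, so a by-arm difference in supportive care would not appear in any planned analysis.

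**What to change.** 1. Reconcile sections 2, 3, 5, 6, 7.5 and 7.12 on whether the study supplies supportive medicines and to which arm or arms. This review does not say which is right.
2. If supply is for Group A only, name the intervention as CRP POCT plus provision of supportive treatment in the objective, in 7.12 and in the planned conclusion.
3. In either case, restore other treatment to 7.15 and 7.21 as a by-arm comparison, using the symptomatic-medication item that 7.5 already lists for the CRF. The table would describe what each arm received; it would not separate the two components.

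The cost is protocol and SAP wording and one extra table, with no added participants or data collection. The downside, if supply is for Group A only, is a narrower claim about CRP testing itself.
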